### 6.1.2 AZD6244 Hyd-Sulfate

**Table 8:** AZD6244 Monotherapy Dose Level Reductions

Dose Level	AZD6244 Dose
Starting Dose	75 mg BID
First Dose Reduction	50 mg BID
Second Dose Reduction	50 mg once daily

**Table 9:** Dosage Modification Criteria for AZD6244-related Toxicities

Event	AE Grade or Observation	Dose modification
Dermatology/Skin	Grade 1 or 2	Maintain dose
	Grade 3 or 4 or intolerable grade 2	Hold AZD6244 until < tolerable grade 2, then reduce 1 dose level and resume treatment  .
	Recurrent Grade 3	Hold AZD6244 until < tolerable grade 2, then reduce 1 additional dose level and resume treatment  .

	Recurrent Grade 3 after 2 dose reductions	Remove patient from study arm.
	Grade 4	Patients with grade 4 rash (i.e. life threatening generalized exfoliative ulceration; erythema multiforme/toxic epidermal necrolysis should be removed from study arm.
V  Diarrhea  (if anti-diarrheal treatment is ineffective)	Grade 1 or 2	Maintain dose; continue anti-diarrheal treatment. Loperamide (4 mg at first onset, followed by 2 mg every 2–4 hrs until diarrhea free for 12 hrs)
	Grade 3 or 4	Hold AZD6244 until < tolerable grade 2, loperamide; reduce 1 dose level and resume treatment  .
	Recurrent Grade 3 or 4	Hold AZD6244 until < tolerable grade 2, loperamide; reduce 1 additional dose level and resume treatment  .
	Recurrent Grade 3 or 4 after 2 dose reductions	Remove patient from study arm.
Hematologic  (neutrophils, platelets, hemoglobin)	Grade 1 or 2	Maintain dose
	Grade 3 or 4	Hold AZD6244 until < grade 2, then reduce 1 dose level and resume treatment.
	Recurrent Grade 3 or 4	Hold AZD6244 until < grade 2, then reduce 1 additional dose level and resume treatment.
	Recurrent Grade 3 or 4 after 2 dose reductions	Remove patient from study arm.
Liver Function  (serum bilirubin, AST, or ALT)	Grade 1 or 2	Maintain dose
	Grade 3 or 4	Hold AZD6244 until < grade 2, then reduce 1 dose level and resume treatment
	Recurrent Grade 3 or 4	Hold AZD6244 until < grade 2, then reduce 1 additional dose level and resume treatment
	Recurrent Grade 3 or 4 after 2 dose reductions	Remove patient from study arm.
Other non-	Grade 1 or 2	Maintain dose

hematological toxicity	Any Grade 2 of concern (e.g., prolonged cardiac, pulmonary, or neurotoxicity, intolerable stomatitis)	Hold AZD6244 until < grade 1, then reduce 1 dose level and resume treatment
	Grade 3 or 4	Hold AZD6244 until < tolerable grade 2, then reduce 1 dose level and resume treatment 
	Recurrent Grade 3 or 4	Hold AZD6244 until < tolerable grade 2, then reduce 1 additional dose level and resume treatment 

1 If event has not improved to < tolerable grade 2 or baseline within < 21 days, patient should be removed from the study.

2 Patients with medically concerning grade 3 or 4 AEs related to AZD 6244 may be taken off study at investigator's discretion.

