## **5.10 Duration of therapy / off treatment criteria**

In the absence of treatment delays due to adverse events, treatment under any of the investigational arms (Erlotinib, AZD6244, MK2206, Lapatinib and Sunitinib) may continue until one of the following criteria applies:

- Disease progression as defined by Section **13**.
- Intercurrent illness that prevents further administration of treatment.
- Delay of treatment due to toxicity of  $\geq 3$  weeks.
- Unacceptable adverse event(s)\*.
- Non-compliance to therapy regimen.
- Pregnancy
- Patient decides to withdraw from the study arm or stop therapy.

- Deterioration of the patient's condition that render further treatment unacceptable in the judgment of the investigator.

\* Patients removed from study arm due to unacceptable adverse events, will continue to be followed in clinic, at least every 4 weeks until all adverse events have resolve to grade I or less.

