## **6 DOSING DELAYS/DOSE MODIFICATIONS**

Patients enrolled in one of the experimental study arms may continue to receive additional cycles of therapy provided that the patient meets the following criteria on Day 1 of each cycle:

- ANC > 1,000/mcL
- Platelets > 100,000/mcL
- Non-hematologic toxicity recovered to < grade 2 (or tolerable grade 2 or baseline)
- No evidence of progressive disease

In the event of an adverse event at least possibly related to the agent, the doses of such agent should be adjusted according to the guidelines shown in the Dose Delays / Dose Modifications tables shown below (Sections 6.1 and 6.2). If an adverse event is not covered in such tables, doses may be reduced or held at the discretion of the investigator for the subject's safety.

Subjects with adverse events that are manageable with supportive therapy may not require dose reductions (e.g., nausea/vomiting ~~may~~ be treated with antiemetics, diarrhea may be treated with loperamide, and electrolyte ~~abnormalities~~ may be corrected with supplements rather than by dose reduction).

Subjects will be withdrawn from the study arm if they fail to recover to CTC Grade 0-1 or tolerable grade 2 (or within 1 grade of starting values for pre-existing laboratory abnormalities) from a treatment-related adverse event within 21 days OR they experience agent related adverse events requiring dose modification despite two previous dose reductions (i.e. would require a 3rd dose reduction) unless the investigator and CTEP monitor agree that the subject should remain in the study arm because of evidence that the patient is/may continue deriving benefit from continuing study treatment (i.e. patient has PR, CR, SD > 3 months). The appropriate reduced dose will be determined after discussion between the principal investigator and CTEP monitor.

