### 6.1.2 MK2206

**Table 10:** MK2206 Monotherapy Dose Level Reductions

Dose Level	MK2206 Dose
Starting Dose	200 mg QW
First Dose Reduction	135 mg QW
Second Dose Reduction	90 mg QW

**Table 11:** Dosage Modification Criteria for MK2206-related Toxicities

Event	AE Grade or Observation	Dose modification
Dermatology/Skin	Grade 1 or 2	Maintain dose
	Grade 3 or 4 or intolerable grade 2	Hold MK2206 until < tolerable grade 2, then reduce 1 dose level and resume treatment  .
	Recurrent Grade 3	Hold MK2206 until < tolerable grade 2, then reduce 1 additional dose level and resume treatment  .
	Recurrent Grade 3 after 2 dose reductions	Remove patient from study arm.
	Grade 4	Patients with grade 4 rash (i.e. life threatening generalized exfoliative ulceration; erythema

		multiforme/toxic epidermal necrolysis should be removed from study arm.
Diarrhea  (if anti-diarrheal treatment is ineffective)	Grade 1 or 2	Maintain dose; continue anti-diarrheal treatment. Loperamide (4 mg at first onset, followed by 2 mg every 2–4 hrs until diarrhea free for 12 hrs)
	Grade 3 or 4	Hold MK2206 until < tolerable grade 2, loperamide; reduce 1 dose level and resume treatment  .
	Recurrent Grade 3 or 4	Hold MK2206 until < tolerable grade 2, loperamide; reduce 1 additional dose level and resume treatment  .
	Recurrent Grade 3 or 4 after 2 dose reductions	Remove patient from study arm.
Hematologic  (neutrophils, platelets, hemoglobin)	Grade 1 or 2	Maintain dose
	Grade 3 or 4	Hold MK2206 until < grade 2, then reduce 1 dose level and resume treatment.
	Recurrent Grade 3 or 4	Hold MK2206 until < grade 2, then reduce 1 additional dose level and resume treatment.
	Recurrent Grade 3 or 4 after 2 dose reductions	Remove patient from study arm.
Liver Function  (serum bilirubin, AST, or ALT)	Grade 1 or 2	Maintain dose
	Grade 3 or 4	Hold MK2206 until < grade 2, then reduce 1 dose level and resume treatment
	Recurrent Grade 3 or 4	Hold MK2206 until < grade 2, then reduce 1 additional dose level and resume treatment
	Recurrent Grade 3 or 4 after 2 dose reductions	Remove patient from study arm.
Other non-hematological toxicity	Grade 1 or 2	Maintain dose
	Any Grade 2 of concern (e.g., prolonged cardiac, pulmonary, or neurotoxicity, intolerable stomatitis)	Hold MK2206 until < grade 1, then reduce 1 dose level and resume treatment
	Grade 3 or 4	Hold MK2206 until < tolerable grade 2, then reduce 1 dose level and resume treatment 

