#### 6.1.3 Lapatinib

**Table 12:** Lapatinib Monotherapy Dose Level Reductions

Dose Level	Lapatinib Dose
Starting Dose	1500 mg daily
First Dose Reduction	1250 mg daily
Second Dose Reduction	1000 mg daily

**Table 13:** Dosage Modification Criteria for Lapatinib -related Toxicities

Event	AE Grade or Observation	Dose modification
Dermatology/Skin	Grade 1 or 2	Maintain dose
	Grade 3 or 4 or intolerable grade 2	Hold Lapatinib until < tolerable grade 2, then reduce 1 dose level and resume treatment  .
	Recurrent Grade 3	Hold Lapatinib until < tolerable grade 2, then reduce 1 additional dose level and resume treatment  .
	Recurrent Grade 3 after 2 dose reductions	Remove patient from study arm.
	Grade 4	Patients with grade 4 rash (i.e. life threatening generalized exfoliative ulceration; erythema multiforme/toxic epidermal necrolysis should

		be removed from study arm.
Diarrhea  (if anti-diarrheal treatment is ineffective)	Grade 1 or 2	Maintain dose; continue anti-diarrheal treatment. Loperamide (4 mg at first onset, followed by 2 mg every 2–4 hrs until diarrhea free for 12 hrs)
	Grade 3 or 4	Hold Lapatinib until < tolerable grade 2, loperamide; reduce 1 dose level and resume treatment  .
	Recurrent Grade 3 or 4	Hold Lapatinib until < tolerable grade 2, loperamide; reduce 1 additional dose level and resume treatment  .
	Recurrent Grade 3 or 4 after 2 dose reductions	Remove patient from study arm.
Hematologic  (neutrophils, platelets, hemoglobin)	Grade 1 or 2	Maintain dose
	Grade 3 or 4	Hold Lapatinib until < grade 2, then reduce 1 dose level and resume treatment.
	Recurrent Grade 3 or 4	Hold Lapatinib until < grade 2, then reduce 1 additional dose level and resume treatment.
	Recurrent Grade 3 or 4 after 2 dose reductions	Remove patient from study arm.
Liver Function  (serum bilirubin, AST, or ALT)	Grade 1 or 2	Maintain dose
	Grade 3 or 4	Hold Lapatinib until < grade 2, then reduce 1 dose level and resume treatment
	Recurrent Grade 3 or 4	Hold Lapatinib until < grade 2, then reduce 1 additional dose level and resume treatment
	Recurrent Grade 3 or 4 after 2 dose reductions	Remove patient from study arm.
Other non-hematological toxicity	Grade 1 or 2	Maintain dose
	Any Grade 2 of concern (e.g., prolonged cardiac, pulmonary, or neurotoxicity, intolerable stomatitis)	Hold Lapatinib until < grade 1, then reduce 1 dose level and resume treatment

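### In Tables 9, 11 and 13 a grade 4 rash falls under both a hold-reduce-resume row and a remove-from-arm row, and no rule says which governs

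*Combined protocol and SAP*

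**What the plan says.** Section 6 gives each drug its own dose-modification table. In Table 9 (Section 6.1.2, AZD6244), the Dermatology/Skin block has a row for "Grade 3 or 4 or intolerable grade 2". Its action is to hold, reduce by one dose level and resume. The last row of the same block is for grade 4 alone: "Patients with grade 4 rash (i.e. life threatening generalized exfoliative ulceration; erythema multiforme/toxic epidermal necrolysis should be removed from study arm".

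Table 11 (MK-2206) repeats the pair. The first row's action is "Hold MK2206 until < tolerable grade 2, then reduce 1 dose level and resume treatment", and the grade 4 row ends "multiforme/toxic epidermal necrolysis should be removed from study arm". Table 13 (Section 6.1.3, lapatinib) does the same, with "Hold Lapatinib until < tolerable grade 2, then reduce 1 dose level and resume treatment" in the first row and, in the grade 4 row, "Patients with grade 4 rash (i.e. life threatening generalized exfoliative ulceration; erythema multiforme/toxic epidermal necrolysis should" followed by removal from the arm.

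The general withdrawal rule in the introduction to Section 6 begins "Subjects will be withdrawn from the study arm if they fail to recover to CTC Grade 0-1 or tolerable grade 2". It sets a 21-day limit and also withdraws a patient who would need a third dose reduction. Section 5.10 lists unacceptable adverse events among the reasons to stop treatment, without naming grade 4 rash.

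**The concern.** A first grade 4 rash meets both rows, and the two actions exclude each other: a patient cannot restart at a lower dose and also leave the arm. An investigator who follows the first row as written would give the drug again after an exfoliative rash or toxic epidermal necrolysis, provided it improved within 21 days. One who follows the grade 4 row would stop the drug for good. Two sites could therefore treat the same event in opposite ways, and each could cite the protocol.

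What is at stake is patient safety and consistent conduct. The response analysis in Section 15.5.2, the PFS definition in Section 13.1.6, the sample size and the error rates do not depend on it.

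**Working it through.** No figure in the plan needs reproducing. The check sets the rows side by side and then looks for a rule that ranks them.

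**Step 1: the rows in each table**

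| Table | Drug | Row covering grades 3 and 4 | Row for grade 4 alone |
|---|---|---|---|
| 9 | AZD6244 | hold, reduce, resume | grade 4 rash: remove |
| 11 | MK-2206 | hold, reduce, resume | grade 4 rash: remove |
| 13 | lapatinib | hold, reduce, resume | grade 4 rash: remove |

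Conflicting rows: 2 per table × 3 tables = 6. Drugs affected: 3 of 5. Each table has 5 toxicity blocks (skin, diarrhea, hematologic, liver, other non-hematological), and only the skin block has a separate grade 4 row. The conflict is confined to that block.

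**Step 2: the search for a ranking rule**

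- Footnote 1, which is marked on the skin hold-and-resume rows, removes the patient only if the event has not improved within 21 days. It does not separate grade 4 from grade 3.
- Footnote 2 allows removal at the investigator's discretion for worrying grade 3 or 4 events. Its marker is on the other non-hematological rows, not the skin rows.
- The introduction to Section 6 gives general discretion over dose only for events the tables do not cover. Grade 4 rash is covered twice.
- Neither withdrawal trigger in Section 6 (no recovery in 21 days, or a third reduction) is met by a first grade 4 rash that improves in time.
- Section 5.10 offers a generic route off treatment and does not say that grade 4 rash must take it.
- The only precedence wording found in Section 6 is in the sunitinib hypertension table (Table 15).

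**Step 3: does the rest of the protocol settle the intent?**

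The recurrence rows point to removal. In the skin block they name grade 3 only; in the other 4 of 5 blocks they name grades 3 and 4. That fits a drafter who took grade 4 rash to be already off the arm. Table 7 points the other way: for erlotinib rash of grade 3 or higher it prescribes hold and reduce, with no grade 4 removal row. Removal is therefore not a rule of the whole protocol that could be read into Tables 9, 11 and 13.

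**Step 4: how much it can matter now**

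- From the closure of the treatment arms on 3/22/2016 to the version date of 01/07/2020 is 1,386 days; 1,386 / 365.25 = 3.8 years.
- No grade 4 rash rate is given at the protocol doses. The nearest figure, in Appendix A, is severe rash in 5 of 42 patients (5/42 = 11.9%) on MK-2206 60 mg every other day, with no CTCAE grade stated. That schedule delivers 60 × 3.5 = 210 mg per week, against 200 mg weekly here, and Section 2.1.4 describes the weekly schedule as the less toxic. Appendix A reports dose-limiting grade 3/4 rash at higher doses (75 and 90 mg every other day, 300 mg weekly). None of this converts into an expected number of patients.

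**The case against.** The strongest reply is that the specific row overrides the general one. The first row covers the whole Dermatology/Skin category, whereas the grade 4 row names one event and one action. On that reading rash leads to removal, other grade 4 skin events are held and reduced, and only the word of exception is missing. This is a reasonable reading, and the recurrence rows support it. It remains an inference, and a dose-modification table for a life-threatening event should not depend on one.

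The other objections bear on weight.

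- The risk lists in Section 7.1.1 do not name toxic epidermal necrolysis for any of these three drugs. Erythema multiforme and Stevens-Johnson syndrome appear for MK-2206 only, among events without sufficient evidence of causation. The worst case may therefore be unlikely, although the grade 4 row itself names it.
- Appendix A says erlotinib should be interrupted or stopped for severe bullous or exfoliative conditions, so Table 7 is not the protocol's full guidance on severe skin toxicity. That is correct, but the wording permits either action and does not rank the rows for the other drugs.
- A note in Section 4.1.1 dated 04/08/14 already describes the treatment arms as closed to accrual. If that date is right, the gap to the version date is about 2,100 days (5.75 years), and 3.8 years is a minimum.
- Section 6 lets the investigator and the CTEP monitor agree to keep a benefiting patient on the arm despite the 21-day or third-reduction trigger. This qualifies those triggers and does not resolve the overlap.

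All four points stand as reasons for giving the matter low weight. None removes the contradiction.

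**Conclusion.** The concern holds. In all three tables a first grade 4 rash is assigned both to restart at a reduced dose and to removal from the arm, and no stated rule chooses between them. The size is one conflicting pair of rows in each of 3 tables, for 3 of 5 drugs. The weight is low. The treatment arms have been closed for at least 3.8 years, the documents identify no patient still on drug, and the number affected may be zero. It matters only for a patient still receiving AZD6244, MK-2206 or lapatinib. The conclusion rests on the written rows alone and needs no assumption about event rates.

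**What to change.** In the first of the two skin rows in Tables 9, 11 and 13, insert *(except grade 4 rash, see Grade 4 row)* directly after the words covering grades 3 and 4. Removal is then the only action for grade 4 rash. Other grade 4 skin events keep a defined action, still subject to the two-reduction limit in Section 6 and its exception for benefiting patients. Deleting the reference to grade 4 from that row would be shorter, but it would leave other grade 4 skin events with no instruction.

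The cost is eight words in one row of each of three tables. The one clinical downside is that a patient who recovers from a grade 4 rash cannot resume the drug.

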### 6.1.2 MK2206

**Table 10:** MK2206 Monotherapy Dose Level Reductions

Dose Level	MK2206 Dose
Starting Dose	200 mg QW
First Dose Reduction	135 mg QW
Second Dose Reduction	90 mg QW

**Table 11:** Dosage Modification Criteria for MK2206-related Toxicities

Event	AE Grade or Observation	Dose modification
Dermatology/Skin	Grade 1 or 2	Maintain dose
	Grade 3 or 4 or intolerable grade 2	Hold MK2206 until < tolerable grade 2, then reduce 1 dose level and resume treatment  .
	Recurrent Grade 3	Hold MK2206 until < tolerable grade 2, then reduce 1 additional dose level and resume treatment  .
	Recurrent Grade 3 after 2 dose reductions	Remove patient from study arm.
	Grade 4	Patients with grade 4 rash (i.e. life threatening generalized exfoliative ulceration; erythema

		multiforme/toxic epidermal necrolysis should be removed from study arm.
Diarrhea  (if anti-diarrheal treatment is ineffective)	Grade 1 or 2	Maintain dose; continue anti-diarrheal treatment. Loperamide (4 mg at first onset, followed by 2 mg every 2–4 hrs until diarrhea free for 12 hrs)
	Grade 3 or 4	Hold MK2206 until < tolerable grade 2, loperamide; reduce 1 dose level and resume treatment  .
	Recurrent Grade 3 or 4	Hold MK2206 until < tolerable grade 2, loperamide; reduce 1 additional dose level and resume treatment  .
	Recurrent Grade 3 or 4 after 2 dose reductions	Remove patient from study arm.
Hematologic  (neutrophils, platelets, hemoglobin)	Grade 1 or 2	Maintain dose
	Grade 3 or 4	Hold MK2206 until < grade 2, then reduce 1 dose level and resume treatment.
	Recurrent Grade 3 or 4	Hold MK2206 until < grade 2, then reduce 1 additional dose level and resume treatment.
	Recurrent Grade 3 or 4 after 2 dose reductions	Remove patient from study arm.
Liver Function  (serum bilirubin, AST, or ALT)	Grade 1 or 2	Maintain dose
	Grade 3 or 4	Hold MK2206 until < grade 2, then reduce 1 dose level and resume treatment
	Recurrent Grade 3 or 4	Hold MK2206 until < grade 2, then reduce 1 additional dose level and resume treatment
	Recurrent Grade 3 or 4 after 2 dose reductions	Remove patient from study arm.
Other non-hematological toxicity	Grade 1 or 2	Maintain dose
	Any Grade 2 of concern (e.g., prolonged cardiac, pulmonary, or neurotoxicity, intolerable stomatitis)	Hold MK2206 until < grade 1, then reduce 1 dose level and resume treatment
	Grade 3 or 4	Hold MK2206 until < tolerable grade 2, then reduce 1 dose level and resume treatment 
	Recurrent	Hold MK2206 until < tolerable grade 2, then reduce 1 additional dose level and resume

	Grade 3 or 4	treatment 
1	If event has not improved to < tolerable grade 2 or baseline within < 21 days, patient should be removed from the study.	
2	Patients with medically concerning grade 3 or 4 AEs related to MK2206 may be taken off study at investigator's discretion.	

In the event of Grade 3 hyperglycemic events (>250 mg/dL) consult with an endocrinologist or other specialist. If glucose levels do not return to grade 1 or lower within one week of appropriate therapy, patients should be considered to have a DLT (dose modification, etc.). Appropriate therapy will usually involve oral antihyperglycemic agents, since the inhibition of glucose transport into the cell by AKT/mTOR inhibitors may render insulin ineffective. The goal of therapy is to keep fasting glucose <150 mg/dL, random blood glucose levels <180 mg/dL, and Hemoglobin A1c <8%. Glucose monitoring should be performed weekly, during the first cycle of therapy, and on day 1 of subsequent cycles, prior to drug administration. Hemoglobin A1c monitoring, for patients requiring treatment of hyperglycemia, should be performed with each cycle of MK-2206 therapy.

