followed with clinical visits at least every 3, 4, or 6 weeks, as defined for each treatment arm; i.e., every 3 weeks for the Erlotinib, AZD6244, and Lapatinib arms; every 4 weeks for the MK-2206 arm; and every 6 weeks for the Sunitinib arm. The time between clinic visits may be extended at the PI's discretion by up to 1 full cycle, for a maximum of 2 cycles between clinic visits (i.e., clinic visits may be extended to every 6 weeks for the Erlotinib, AZD6244, and Lapatinib arms; every 8 weeks for the MK-2206 arm; and every 12 weeks for the Sunitinib arm). If the frequency of clinic visits is extended, laboratory tests will not be required nor samples collected until the next clinic visit. Re-staging imaging will be performed at the end of every two cycles as defined for each treatment arm; i.e., every 6, 8, or 12 weeks +/- 1 week. See Section 5.9.2 for details. The patients will continue on the selected arms until disease progression.

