## **5.9 Protocol Evaluation**

5.9.1 Prior to each treatment cycle (please refer to Section **5.3** for definition of a cycle):

5.9.1.1 SOAP progress note.

5.9.1.2 Laboratory examination:

5.9.1.2.1 Hematological Profile: CBC with differential and platelet count.

5.9.1.2.2 Biochemical Profile: Sodium, potassium, chloride, CO2, BUN, creatinine, glucose, AST, ALT, alkaline phosphatase, bilirubin, albumin, total protein, LDH, calcium, phosphorous and magnesium.

5.9.1.3 Vital signs including weight.

5.9.2 Restaging and Imaging:

Restaging will be performed at the end of every two cycles, +/- 1 week, as defined for each treatment arm. Therefore, restaging will be performed every 6 weeks +/- 1 week for the Erlotinib, AZD6244, and Lapatinib arms; every 8 weeks +/- 1 week for the MK-2206 arm, and every 12 weeks +/- 1 week for the Sunitinib arm. Imaging modalities will consist of CT or MRI, as appropriate for disease evaluation. The use of FDG-PET will be allowed but it would be considered exploratory and its results will not be used for treatment decisions.

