## 12 STUDY CALENDAR

Baseline evaluations are to be conducted within 1 week prior to start of protocol therapy. Scans and x-rays must be done <4 weeks prior to the start of therapy. In the event that the patient's condition is deteriorating, laboratory evaluations should be repeated within 48 hours prior to initiation of the next cycle of therapy. The study calendar does not apply to individuals enrolled for EGFR germline mutation testing only; please refer to Section 5.6 for testing and follow-up of these individuals.

	Screening – Part 1 Molecular Profiling and Correlative Studies	Screening – Part 2 Treatment Arm Eligibility (see Section 3.3)	Treatment Cycles (see Section 5.3; clinic visits may be extended to every 6 weeks for the Erlotinib, AZD6244, and Lapatinib arms; every 8 weeks for the MK-2206 arm; and every 12 weeks for the Sunitinib arm)	Off treatment
Biopsy for molecular profiling 	X		Upon disease progression per section 5 (optional)	
Targeted therapies 			See section 5 for details regarding agent administration and scheduling	
Informed consent	X		N/A	
Demographics	X			
NOS arm data 		X		
Medical history 		X	Every clinic visit	X
Concurrent Meds 		X	Every clinic visit	X
NIH Advance Directives Form 	X			
Physical exam 		X	Every clinic visit	X
Vital signs 		X	Every clinic visit	X
Height 		X	N/A	
Weight 		X	Every clinic visit	X
Performance status 		X	Every clinic visit	X
CBC w/diff, plts 		X	Prior to each clinic visit	X
Serum chemistry 		X	Prior to each clinic visit	X
PT, aPTT 		X		X
Urinalysis 		X		X
EKG 		X	As clinically indicated	X
BP 			Weekly during cycle 1	
ECHO/MUGA 		X	Every other treatment cycle	
Adverse event evaluation 			X-----X	X
Tumor measurements 		X	Approximately every 6, 8, or 12 weeks, as defined for each treatment arm. See Section 5.8.2 for details. Documentation (radiologic) must be provided for patients removed from study arm for progressive disease.	X

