			
:Sodium, potassium, chloride, CO2, BUN, creatinine, glucose, AST, ALT, alkaline phosphatase, bilirubin, albumin, total protein, LDH, calcium, phosphorous and magnesium.
 
:Serum pregnancy test (women of childbearing potential).
 
: Required only for patients enrolled on a Sunitinib treatment arm, per section 6.2.1.
 
: Required only for patients enrolled on a Lapatinib treatment arm, per section 6.1.5.
 
: Required for patients enrolled on a Sunitinib treatment arm who have known cardiac dysfunction at study entry and/or clinically observed adverse cardiac events.
 
: For patients enrolled on the MK-2206 arm, who require treatment of hyperglycemia per section 6.1.2, HgbA1c, monitoring should be performed with each cycle of MK-2206 therapy
 
: 1 5ml EDTA tube (purple top) and 1 urine sample collected in a (yellow top) urine tube. Page [name] [name] for pick up.
 
: 1 10ml Sodium Heparin Tube (green top). Call [name] for pick up at [contact].
 
: N/A for patients assigned to the NOS arm.
 
: Required only for the patients assigned to the NOS arm.
 
: Including any other procedures necessary to do the biopsy, as clinically indicated.
 
: Correlative Studies: See Section 9 for details.
 
: Selected patients only (see Section 5.6). Patient must meet eligibility requirements for EGFR germline mutation testing and have signed a separate consent form.
 
: As indicated in section 16.3, all subjects <math>\geq</math> age 18 will be offered the opportunity to complete an NIH advance directives form. This should be done preferably at baseline but can be done at any time during the study as long as the capacity to do so is retained. The completion of the form is strongly recommended, but is not required.
	

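### The Section 5.3 visit extension waives laboratory tests that Sections 5.9.1, 6 and 6.1.2 require each cycle, and the weekly cycle 1 glucose for MK-2206 has no place on the schedule

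*Combined protocol and SAP*

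**What the plan says.** Two sections carry the number 6.1.2; the relevant one is headed MK2206. The text below Table 11 sets the glucose schedule: "Glucose monitoring should be performed weekly, during the first cycle of therapy, and on day 1 of subsequent cycles, prior to drug administration". The sentence that follows limits HbA1c monitoring to patients who need treatment for hyperglycemia. The glucose sentence carries no such limit.

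Elsewhere, glucose appears only as one item of the chemistry profile. Section 5.9.1 times that profile "Prior to each treatment cycle". The Section 12 calendar times serum chemistry "Prior to each clinic visit". Section 5.3 sets MK-2206 visits at least every 4 weeks. It lets the principal investigator lengthen the interval "for a maximum of 2 cycles between clinic visits", which is 8 weeks in this arm, and adds: "If the frequency of clinic visits is extended, laboratory tests will not be required nor samples collected until the next clinic visit". No arm or test is excepted.

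The calendar has no glucose row. Its only MK-2206 glycemic entry is footnote 6, for patients "who require treatment of hyperglycemia per section 6.1.2, HgbA1c, monitoring should be performed with each cycle of MK-2206 therapy". It does carry a comparable check for another arm: a blood pressure row, "Weekly during cycle 1", which footnote 3 marks as "Required only for patients enrolled on a Sunitinib treatment arm, per section 6.2.1".

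**The concern.** There are two problems, and the second is the clearer one.

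First, the cycle 1 glucose checks on days 8, 15 and 22 are asked for in the dose-modification section but appear in no visit schedule, calendar row or home-monitoring instruction. Footnote 6 cites Section 6.1.2 and takes over its HbA1c sentence, but not the glucose sentence just before it.

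Second, the Section 5.3 waiver is an affirmative statement that tests are not required. It therefore contradicts other operative text, and does not merely leave out a detail. Section 5.9.1 wants blood count and chemistry before every cycle. Section 6 allows another cycle only if day 1 neutrophils exceed 1,000/mcL and platelets exceed 100,000/mcL, which needs a blood test. Section 6.1.2 wants day 1 glucose for MK-2206. No clause was found that says which section governs.

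At stake are later detection of grade 2 or higher hyperglycemia, and a hyperglycemia count that depends on the schedule a site followed, because a transient rise can fall between checks 4 weeks apart. The MK-2206 adverse event list in Section 7.1.1.3 places hyperglycemia in the likely category (above 20%). Section 6.1.2 also has a one-week recovery rule for grade 3 events, which cannot start until the rise is found.

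**Working it through.** The plan gives no figure to reproduce, so the check is a count of schedule days.

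Inputs:
- MK-2206 is dosed weekly in a 4-week cycle (5.7.1.3). The diary in 18.2.2 puts doses on days 1, 8, 15 and 22 of 28.
- Glucose under 6.1.2: weekly in cycle 1, then day 1 of each later cycle.
- Glucose under 5.9.1 and the calendar: once per cycle or visit, with visits every 4 weeks.
- Extension under 5.3: visits every 8 weeks, with no laboratory tests between them.

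Cycle 1: 6.1.2 gives days 1, 8, 15 and 22 (4 checks); the schedule gives day 1 (1 check). So 4 − 1 = 3 are unscheduled.

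First check after the first dose: day 8 under 6.1.2 (1 dose given) against day 29 under the routine schedule (4 doses given), which is 29 − 8 = 21 days later.

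Six cycles, reading each source on its own:

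| Source | Glucose days | Checks |
|---|---|---|
| 6.1.2 | 1, 8, 15, 22, 29, 57, 85, 113, 141 | 9 |
| 5.9.1 and calendar, 4-week visits | 1, 29, 57, 85, 113, 141 | 6 |
| 5.3 extension after the day 29 visit | 1, 29, 85, 141 | 4 |
| 5.3 extension from cycle 1 | 1, 57, 113 | 3 |

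With routine visits all 5 later day 1 checks are kept, and only days 8, 15 and 22 are missing. The waiver removes alternate day 1 checks: 3 of 5 remain if the extension starts after day 29, and 2 of 5 if it starts in cycle 1.

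The contradiction shows on day 29 for a patient whose visits are extended from cycle 1. Section 5.3 requires no tests. Section 5.9.1 requires blood count and chemistry, including glucose. Section 6 requires neutrophils and platelets. Section 6.1.2 requires glucose. These cannot all be followed. The calendar ties chemistry to visits, so it goes along with 5.3. Without the glucose item, the same conflict arises in the other arms, where 5.3 allows visits every 6 weeks (erlotinib, AZD6244, lapatinib) or every 12 weeks (sunitinib).

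**The case against.** Section 6.1.2 is operative text, visits are set at a minimum frequency, and nothing in 5.9.1 or the calendar forbids extra tests. A site that reads the whole protocol can follow 6.1.2. This stands: for cycle 1 the fault is a missing provision, and a reader who infers that the protocol withdraws the weekly checks goes further than the text.

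The calendar is a summary. Appendix H asks for sunitinib blood pressure at least every 2 weeks after cycle 1, and Section 6.1.4 asks for repeat ejection fraction measurements on lapatinib; neither is a calendar row. This also stands. The absent row does not show that the glucose check was deliberately dropped, and the gap is not peculiar to MK-2206.

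The paragraph in 6.1.2 opens with grade 3 hyperglycemia, so the glucose sentence might apply only to affected patients. This is possible but less natural: the sentence speaks of the first cycle and of testing before dosing, and the narrower limit is attached to HbA1c alone.

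A reader might infer that MK-2206 patients would go without a glucose check until day 57, after 8 doses. The documents do not support that as the expected course. It needs an extension from cycle 1 and a site that disregards both the chemistry in 5.9.1 and the day 1 criteria in Section 6, which would prompt a blood draw on day 29 although they do not name glucose. Nor does the waiver remove all later checks.

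The clinical consequence is limited. Section 2.1.4 reports no significant hyperglycemia so far in phase I and less toxicity on the weekly schedule. Appendix A describes episodes on every-other-day dosing as generally mild and transient, with one grade 3 case and one grade 4 case, the latter in combination with erlotinib. Uncontrolled diabetes is excluded (3.2.2.5), and grade 1 events need not be collected (7.4).

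None of this reconciles 5.3 with 5.9.1 and Section 6.

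**Conclusion.** The point holds at minor severity. The Section 5.3 waiver contradicts 5.9.1 and Section 6 in every treatment arm, and 6.1.2 as well for MK-2206. Separately, 3 of the 4 cycle 1 glucose checks that 6.1.2 asks for have no scheduled visit or calendar row.

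The counts assume 28-day cycles without delay, the all-patients reading of the glucose sentence, and no checks added locally. The extension figures also assume that 5.3 is followed where it conflicts with other sections, and that the investigator uses the extension at all.

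A reader might infer that trial results are compromised. The documents do not support that: sample size and the response analysis do not use glucose, and Section 15 plans no hyperglycemia analysis. Sections 16.4 and 16.5 state that the treatment arms are closed, so what remains concerns any patient still on drug, the description of safety data, and reuse of the text.

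**What to change.** 1. Amend Section 5.3 so that a longer visit interval does not waive the laboratory tests required before each cycle, including day 1 glucose for MK-2206, and allow a local laboratory. Exempting glucose alone would leave the conflict with Section 6 in place.
2. Add an MK-2206 calendar row, in the form of the sunitinib blood pressure row: glucose weekly in cycle 1 and on day 1 of each later cycle, before dosing.
3. Where MK-2206 hyperglycemia counts are reported, state which glucose schedule was followed. This is useful even with the arms closed.

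The cost is one calendar row, one amended sentence in 5.3 and one sentence in the safety report. For a treated patient it is 3 further glucose tests in cycle 1 and a local blood draw in cycles without a visit. The ceiling for cycle 1 is 3 disease strata × 20 patients = 60 patients, and 60 × 3 = 180 tests. Section 6.1.2 already calls for all of them, and Section 15.2 expects that enrollment may be far lower.
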